143 incorporating clinician advise to quit, which has been shown to increase quit rates. If implemented  
144 together, these intervention could have a synergistic effect (see Figure 1) whereby the interventions  
145 operate at different levels of influence to mutually reinforce each other. Their combined effect has great  
146 potential to increase the proportion of appropriate referrals (i.e., eligible and ready patients) to the QL,  
147 increase the likelihood of successful patient contact and enrollment, positively affect patients' ratings of  
148 the experience, and support positive movement towards cessation.

Figure 1. AAC and TMCP conceptual model

150

151 **Study goals and objectives**

152 1. Improve delivery and documentation of smoking cessation advice and assistance to socially and  
 153 economically disadvantaged patients using an Ask-Advise-Connect approach integrated into the EHR.  
 154 2. Test the effect of combining the TMCP with AAC on process outcomes, QL referral outcomes and  
 155 smoking outcomes.  
 156 3. Examine the narratives of subgroups of individuals to better understand the referral experience and  
 157 identify ways to improve it.

158

159 **Study Design and Timing.** This study involves two interventions. This report is focused on the TMCP  
 160 intervention and the AAC information is provided for context. The full report will be publically available  
 161 on the PCORI website after the 12-month embargo period passes.

[figure not shown]
162 The AAC was conducted first at the clinic-level and the TMCP was conducted second at the clinician-  
 163 level. It also includes qualitative data collection to complement the quantitative evaluations. Figure 2  
 164 illustrates the three main data collection sources (EHR, patient surveys, and in-depth interviews) and the  
 165 three time periods of data collection (pre-AAC, AAC-only, and AAC+TMCP). The 3-month period before  
 166 the AAC intervention represented a pre-AAC control period (baseline). Both interventions were  
 167 implemented using a stepped wedge design, as indicated in Figure 2. The start date represents the date

168 of the first clinic's exposure to the interventions. The step graphic between each condition represents  
169 the starting points for each of the clinics' exposure to the interventions. This design allowed us to test  
170 the additional impact of TMCP beyond the gains realized via AAC across all of the clinics by the end of  

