171 the step-wedge implementation. On a rolling basis, data collection indicated the intervention exposure  
172 statuses for each clinic and assessed visit level process outcomes.

[figure not shown]
173 Figure 3 provides more detail about the timing of the AAC and the TMCP intervention  
174 implementation at each of the 8 sites. AAC was the first intervention implemented, and the AAC training  
175 at the first clinic was conducted on February 15, 2017. This training was then conducted at the other  
176 seven clinics at approximately 2-week intervals, but the timing of the training was not randomized.  
177 Trainings were scheduled during regularly scheduled monthly staff meetings for each clinic. The training  
178 date was noted such that a period of pre- and a period of post-training could be defined for each clinic.  
179 Approximately 6 months after the implementation of the AAC in the last site, the TMCP intervention was  
180 implemented, again in a stepped pattern.

181 For the TMCP, the eight clinics were randomized to an implementation time point using the  
182 following approach. A single digit number was assigned to each site. A list of 100 random single digit  
183 numbers was generated and using this list, as a site number came up in the random list it was assigned  
184 the next sequential time point. We encountered two anomalies with randomization of the sites. First,  
185 after implementing the AAC intervention, the site that was randomized to receive the TMCP training  
186 first lost their practice manager. MetroHealth requested that we delay the implementation of the TMCP  
187 in that site due to challenges with daily operations until a new practice manager was effectively in place.  
188 This site was moved to be last. Second, also after the implementation of the AAC intervention, one of  
189 the sites closed. A replacement site was identified to receive the AAC intervention and was included as  
190 the last site for training for the TMCP. The TMCP implementation time points were scheduled as close to  
191 1-month intervals as possible. The first clinic received the TMCP training on October 25, 2017. The  
192 amount of time a clinic was in any one of the three defined study conditions varied but is accounted for  
193 in the analyses.

194 Figure 2. Schema of data collection time points (for EHR, surveys, and in-depth interviews) across all  
195 sites.

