#### Debriefing about the training and follow-up

Following the completion of the web-module and the skills practices, the providers re-grouped with the research team to debrief about their experiences. Feedback on format, length of training, processes, content etc. were discussed as well as the perceived value overall. Approximately one month after the TMCP training participating clinicians were sent follow-up messages through the EHR that 1) offered reminders about the TMCP, 2) encouraged clinicians to use the TMCP, and 3) provided instruction for using the tobacco cessation flowsheet. Clinicians were invited to respond to messages with questions and or feedback.

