### Measures

Clinician characteristics gathered from the health system included: sex, degree (MD, DO, NP), specialty and years since last clinical training. Patient characteristics including sex, race, ethnicity, insurance type and smoking status, were drawn from the EHR.

TMCP-specific variables include training participation, online learning module completion and quiz score. Use of the TMCP flowsheet by clinicians during visits was measured for 6-months after training to indicate use of the TMCP. Clinician's documentation of any portion of the TMCP flowsheet was counted as 'use'.

Outcome measures include contact by the QL or FFS among those patients that accepted a referral and provision of brief advice. Secondary outcomes include medication orders (i.e. varenicline, bupropion or nicotine replacement therapy) enrollment among those referred to cessation support (QL or FFS), and quit attempts. For this study, a quit attempt is defined as a change in smoking status from current smoker to former smoker and documentation of a quit date in the EHR. Quit attempts are evaluated for all smokers.

We report the rates of Ask, Advise, Assessment of readiness to quit and acceptance of a referral (Connect) to tobacco cessation assistance for the AAC intervention (AAC only) period and the time period after the TMCP intervention (AAC+TMCP). Each of these indicators is measured from discrete fields in the EHR. As shown in Figure 1, the timing of the AAC and the TMCP intervention implementation and the time periods between the two interventions varied.

We assessed patients' experiences with the clinic's processes. The survey samples included at least 17 smokers from each of the eight sites for the AAC only and the AAC+TMCP study periods. Patients who attended a primary care visit during a specified period were invited to complete the survey by web or phone, depending on the participant's preferred contact method. The survey included 11 items about being treated with respect, feeling listened to, and whether the advice was helpful. Responses were measured using a 5- point Likert scale rating from excellent to poor.

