#### Statistical analyses

We describe clinician characteristics and patient visits during the study period, and participation in the training and uptake of the TMCP as documented by flowsheet usage. Analyses compared adjusted rates for the AAC+TMCP intervention to AAC only period using a generalized estimating equation (GEE) approach, with robust estimation of variances. Specifically, we modeled the log odds of a particular outcome of interest for a particular patient as a function of intervention status (AAC only vs. TMCP + AAC) at each time point, incorporating random practice site and clinician effects. Three analyses were conducted: 1) intent to treat, 2) per protocol (i.e. clinicians that participated in the TM training), and 3) per documented use of the TMCP approach in a visit. We report rates of performance, odds ratios (OR) and 95% confidence intervals (95% CI). We used 10% as a minimally important difference. Data analyses were performed April 2019 - August 2020. Because this was an educational intervention for clinicians, all of whom ultimately received the training, neither the clinicians nor the study team could be blinded to the group assignment; this design also made it impossible to blind the analyst to group assignment.

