### **Follow-up**

Follow up for adverse effects of the intervention are not applicable. Performance feedback reports were provided at 1, 2, and 3 months post training and provided an outlet for participating clinicians to contact the study staff with questions or comments.

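### The stated model names no calendar-time term, so if it was followed as written a sustained common trend would bias the TMCP odds ratio in either direction

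*Combined protocol and SAP*

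**What the plan says.** The Statistical analyses section describes a GEE logistic model with robust variances that compares AAC+TMCP with the AAC-only period. The log odds of an outcome are modelled "as a function of intervention status (AAC only vs. TMCP + AAC) at each time point, incorporating random practice site and clinician effects". The compared rates are called adjusted, but no adjusters are listed. The Project summary mentions generalized linear models without giving terms.

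The nearest thing to a time adjustment is in Study Design and Timing: the "amount of time a clinic was in any one of the three defined study conditions varied but is accounted for" in the analyses. No method is given.

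The same section gives the purpose of the design, which is to test "the additional impact of TMCP beyond the gains realized via AAC across all of the clinics by the end of" the stepped roll-out. It also gives the timetable. AAC training began on 15 February 2017 and reached the other sites at steps of about two weeks. "The first clinic received the TMCP training on October 25, 2017", and the other sites followed at steps of about a month. The Study sample section ends data collection in April 2019.

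Three further statements bear on the remedy:
- Debriefing about the training and follow-up: "Approximately one month after the TMCP training participating clinicians were sent follow-up messages through the EHR".
- Follow-up: "Performance feedback reports were provided at 1, 2, and 3 months post training".
- Measures: "Use of the TMCP flowsheet by clinicians during visits was measured for 6-months after training to indicate use of the TMCP".

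On timing, the Statistical analyses section says: "Data analyses were performed April 2019 - August 2020".

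**The concern.** In a stepped-wedge design the intervention condition is on average later than the control condition at every site. Site and clinician effects remove stable differences in level between clusters. They do not remove a change over time that all clusters share. What separates such a change from the intervention is comparing sites in different conditions at the same calendar time, and that needs a time term.

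None of the wording supplies one. The reference to each time point says when intervention status is read. The statement about time in each condition concerns duration, not calendar date.

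A trend is plausible here. AAC was itself new, so its rates could still have been rising or fading when TMCP began. Problems anticipated also warns that six-monthly EHR upgrades could disrupt the tools behind the intervention. At stake is whether the TMCP odds ratio, for the primary outcome and every other outcome modelled this way, is a stepped-wedge estimate or a before/after estimate.

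**Working it through.** The plan gives no power, sample-size or bias figure to reproduce. The check rebuilds the calendar and asks what the stated model returns when TMCP does nothing.

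**Inputs from the documents.** First AAC training 15 February 2017, with 14-day steps. First TMCP training 25 October 2017, with one-month steps. Eight sites; data to 30 April 2019. Starting rate 42%: Rationale & background information gives this as an upper bound on Quitline contact in prior studies.

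**Assumptions.** Drift sizes are assumed. Exact site dates are in Figure 3, which is not shown, so spacing comes from the text, and sites are taken in the same order for both interventions. Volume is even over time. The window for the TMCP contrast is not stated, so two are used: all data, and six post-training months (the period the plan gives for flowsheet use only).

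**Step 1: calendar.** Month 0 is 15 February 2017. For site i = 0 to 7, AAC starts at 0.46i, TMCP starts at 8.28 + i, and data end at 26.41. Weighting each site's midpoint by its length:
- Mean time of AAC-only data: 6.9 months.
- Mean time of AAC+TMCP data: 18.9 months (all data), or 8.28 + 3.5 + 3 = 14.8 (six months).
- Gap: 18.9 - 6.9 = 12.0 months, or 14.8 - 6.9 = 7.9 months.

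**Step 2: hand approximation.** Let p(t) = 0.42 + b*t with no TMCP effect and b = +0.005 per month. The AAC-only mean is 0.42 + 0.005 x 6.9 = 0.4545, and the AAC+TMCP mean is 0.42 + 0.005 x 18.9 = 0.5145. OR = (0.5145/0.4855) / (0.4545/0.5455) = 1.27.

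**Step 3: model fit.** A logistic model with intervention status and site effects, fitted to the expected rates, gives:

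| Assumed drift, points per month | OR, all data | OR, six months |
|---|---|---|
| +0.5 / -0.5, sustained | 1.28 / 0.76 | 1.18 / 0.84 |
| +0.25 / -0.25, sustained | 1.13 / 0.88 | 1.09 / 0.92 |
| +0.5 / -0.5 in each site's first six AAC months, then flat | 1.04 / 0.96 | 1.04 / 0.96 |

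With calendar quarter added, the sustained-drift results are 0.98 to 1.02. A differently shaped trend, +/-2% per month in the odds, gives 1.27-1.28 / 0.78 without time on all data and 1.00 with linear time.

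For starting rates of 20% to 60%, sustained drift of +/-0.5 spans 1.28-1.38 and 0.58-0.78 (all data), or 1.18-1.24 and 0.72-0.85 (six months). The 0.58 extreme needs a 20% rate to fall to 20 - 0.5 x 26.4 = 6.8%.

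A spurious 10-point difference needs 10/12.0 = 0.83 point per month (all data) or 10/7.9 = 1.27 (six months), sustained. The plan's minimally important difference is 10%, without saying whether that is absolute or relative.

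**Step 4: does the usual remedy hold if the TMCP effect changes after training?** Assume a maximum effect of +10 points, a 42% start and no drift:

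| Pattern and window | True average OR | No time | On/off + quarter | Time-since-training bands + quarter |
|---|---|---|---|---|
| Builds over 6 months, all data | 1.38 | 1.38 | 1.10 | 1.37 |
| Fades, 6-month time constant, all data | 1.16 | 1.17 | 1.41 | 1.19 |
| Builds, six months | 1.22 | 1.22 | 1.09 | 1.22 |
| Fades, six months | 1.29 | 1.29 | 1.39 | 1.30 |

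With drift of +/-0.5 added to the build-up in the six-month window, the true ORs are 1.22 / 1.24. The model without time gives 1.44 / 1.04, on/off + quarter gives 1.11 / 1.07, and bands + quarter gives 1.25 / 1.20.

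**The case against.** **The document is a retrospective summary.** The analyses were finished before its last update, a fuller report is mentioned, and the references to adjusted rates and to accounting for time in condition leave room for a time term that was not written down. This stands as a limit. A reader might infer that the trial's analysis omitted calendar time, or that its odds ratio is biased. The documents support neither: they show what the specification names, not what was fitted.

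**The drift is assumed.** This also stands. AAC-only ran for at least six months by the plan's account, so early change may have levelled off, and then the distortion is small (1.04 / 0.96). The 42% is an upper bound for Quitline contact, whereas the Measures section also counts the in-house programme.

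**The remedy can do harm.** This stands in part. If the TMCP effect builds or fades and there is no drift, the model without time is nearly right and the on/off model with quarter is not. The reminders and feedback in the first three months make a changing effect a real possibility. Replacing the main model with a time-adjusted on/off model, with results known and an unblinded analyst, would be wrong. But the model without time fails when drift is present, so leaving it alone is no answer.

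**Non-concurrent data.** A reader might infer that data from months when all sites share one condition are of no use. That does not follow: without a time term all months feed the same contrast, and with one those months still help to estimate site effects.

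**Conclusion.** The concern holds as a defect of the stated model. Followed as written, that model cannot separate TMCP from a sustained change common to all sites, and the bias takes the sign of that change. The size depends on the assumed trend: an odds ratio from about 0.76 to 1.28 on all data, or 0.84 to 1.18 with six post-training months, at 0.5 point per month sustained from a 42% start, and close to 1 if early AAC change levels off. The direction of the argument rests only on the one-way crossover and the listed terms. The figures rest on the rebuilt calendar and the assumed drift. The documents do not show that a trend occurred. Until the time term is stated, a reader cannot tell which kind of estimate the odds ratio is.

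**What to change.** 1. State which calendar-time term, if any, was fitted for each outcome. If one was, reporting it settles the point.
2. If none was, re-run each outcome model with intervention status, calendar quarter, site and clinician. Linear month is the minimum, and it relies on the trend being straight. Report the result beside the existing estimate, labelled as added after the results were known.
3. Base any claim of a TMCP effect beyond AAC on the time-adjusted estimate, and describe the estimate without time as before/after.
4. Alongside it, report an analysis by time since training: monthly bands for post-training months 1 to 6 plus calendar quarter, giving each band and their average. In the six-month window this stayed within 0.04 of the true odds ratio in every scenario run at a 42% start. On all data it does less well: 1.31 against a true 1.41 with build-up and drift of -0.5.

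**Cost.** The data are already held, so the price is precision and one assumption. In a simulation with assumed inputs (15 referrals per site-month; logit SDs of 0.3 for site, 0.3 for clinician and 0.1 for site-quarter), the standard error of the log odds ratio on all data rises from 0.081 to 0.148 with linear month (0.148/0.081 = 1.8 times) and to 0.173 with quarter (2.1 times). In the six-month window it rises from 0.100 to 0.189 with quarter (1.9 times) and to 0.216 with bands and quarter (2.2 times). Bands on all data cost more: 0.285/0.081 = 3.5 times. The on/off model with time also assumes a constant TMCP effect, which step 4 checks.

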## Research methods

### Participating sites and randomization

Eight community-based primary care practices in a large safety-net healthcare system in Cleveland Ohio participated in this stepped wedge comparative effectiveness study. Using a random number list generated by the study analyst, the sites were randomized to separate intervention time points (1-month intervals) in which all clinicians (MD, DO, NPs) who spend 40% or more of the work week providing patient care were scheduled to attend the TMCP training. The health system requested that the intervention be implemented first in one site. The remaining 7 sites followed the randomization procedure. The principal investigator informed each clinical director of the site's assigned time point and scheduled a training date.

Prior to the baseline period for this study, all eight clinics engaged in an AAC system change initiative to improve the provision of tobacco cessation support. The systems change engaged MAs/RNs to use an EHR supported AAC strategy. The MA/RN role, which normally included Asking about tobacco status, expanded to: 1) Using a brief scripted phrase, to Advise those who use tobacco to quit; 2) Assessing interest in quitting tobacco in the next 30 days; 3) for patients interested in quitting now, asking if they would like assistance to quit from a coach or counselor; and 4) for those choosing assistance, Connecting the patient by an electronic referral (e-referral) sent to either the Ohio Quitline (QL) or to the in-house Freedom from Smoking (FFS) program. Eligibility for free QL services included being aged 18 or older with Medicaid or no insurance, or being pregnant. The QL included up to 5 telephonic counseling sessions and access to web and online chat support. The QL offers nicotine replacement therapy (NRT), if indicated, and with approval from the referring clinician, the NRT is mailed to the patient. Individuals not eligible for the QL were referred to the in-system FFS program – an in-person 8-session group tobacco cessation class offered by the healthcare system. The EHR automatically assessed patient eligibility with payer data and generated the correct referral order in a

process that was seamless for both the MA/RN and the patient. The AAC serves as the comparator for the TMCP.

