#### Development of document flowsheet

Document flowsheets are EHR tools used to document information in a structured manner. The TMCP flowsheet outlines the steps and phrases for the TMCP for clinicians to use as a guide with patients, eliminating the need to memorize each sequential TMCP step. The flowsheet is also a simple standardized tool to record patient responses with minimal clinician effort. With this tool, both the delivery of TMCP and the recording of patient information are done simply and result in retrievable records for future care.

During the skills training each clinician was shown how to use the TMCP flowsheet and had it added to his/her EHR tool shortcuts. Clinicians were asked to use the flowsheet during the skills practice scenarios to gain experience and comfort with its features. As needed, coaches could address any difficulty clinicians had using the flowsheet during the feedback period after a skills practice. An EHR tobacco cessation order set could be used by providers to order tobacco cessation medication and to order QL or FFS classes and was also reviewed during skills practice.

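### For the steps delivered by MAs/RNs, the model has no MA/RN effect and the robust variance has no stated cluster level; if MA/RN staffing changed between periods, a model-based or clinician-clustered interval would be too narrow

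*Combined protocol and SAP*

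**What the plan says.** The Statistical analyses section compares AAC+TMCP with AAC only "using a generalized estimating equation (GEE) approach, with robust estimation of variances", modelling the log odds of each outcome and "incorporating random practice site and clinician effects". One dependence structure serves all outcomes. The cluster level of the robust variance is not given, no small-sample correction is named, and no calendar-time term is clearly specified.

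Under Participating sites and randomization, the AAC steps belong to support staff: "The systems change engaged MAs/RNs to use an EHR supported AAC strategy". The next sentence begins "The MA/RN role, which normally included Asking about tobacco status, expanded to" and goes on to add scripted advice, assessment of interest in quitting and the e-referral. Referral is not theirs alone. Under Development of document flowsheet, "An EHR tobacco cessation order set could be used by providers to order tobacco cessation medication and to order QL or FFS classes".

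The Measures section gives the outcome measures as "contact by the QL or FFS among those patients that accepted a referral and provision of brief advice". It also reports the Ask, Advise, Assess and Connect rates for both periods. It names no MA/RN identifier or staffing variable, and does not say whether brief advice is scored from the MA/RN's entry, the clinician's, or either. The Project summary names QL contact as the primary outcome.

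**The concern.** For Ask, Advise and Assess, the person who performs and records the step is an MA/RN, and nothing in the model represents that person. Data at the first TMCP site run about 18 months beyond its training date (25 October 2017 to April 2019). An MA/RN who left before training, or joined after it, contributes to one condition only, so that person's habit of advising or recording falls into the TMCP contrast. A clinician effect does not remove this if the same MA/RN rooms patients for several clinicians, because the shift is then shared across clinicians.

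The result is extra noise in the estimate, not a bias in a known direction. If the interval leaves that noise out, the analysis can report a TMCP effect on advice or on a process rate when only the staffing changed. Clinician clustering is a plausible reading of the plan, because Study Design and Timing describes TMCP as conducted at clinician level, although the sites were randomised.

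**Working it through.** The documents give no power calculation, intraclass correlation (ICC), MA/RN count, MA-clinician pairing or MA/RN turnover, so there is no planned figure to reproduce. The results below are conditional ranges.

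**Inputs from the documents.** 8 sites and 60 clinicians (Study sample); first TMCP training 25 October 2017, then steps of about one month (Study Design and Timing); data to April 2019 (Study sample); 95% intervals (Statistical analyses). The timeline was coded as 24 months, with TMCP starting in months 8 to 15.

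**Assumed inputs.** Advice rate 0.60; 10 or 30 smoker visits per clinician-month; site ICC 0.01; clinician ICC 0.03; MA ICC 0 to 0.20; 6 or 10 MAs per site; MA turnover 0 to 4% a month; MAs either rotating across a site's clinicians or paired with one; month terms absent or present.

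**Step 1: mechanism.** Let MA *m* have effect *b_m* with variance σ², and let *w_m0* and *w_m1* be that MA's share of visits before and after training. The site contrast then contains Σ(*w_m1* − *w_m0*)*b_m*, with variance σ²Σ(*w_m1* − *w_m0*)². If the shares do not change, this is zero however much MAs differ.

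**Step 2: hand example.** Take 6 MAs with equal shares, one replaced between periods, MA ICC 0.10 and rate 0.60. Then σ² = 0.10 × 0.60 × 0.40 = 0.024. The leaver and the joiner each contribute (1/6)², so the added variance is 0.024 × 2/36 = 0.00133 per site, an SD of 0.0365. In a simple before-after average over 8 sites this is 0.0365/√8 = 0.013 on the risk scale. More visits do not reduce it.

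**Step 3: stepped-wedge calculation.** A linear-probability GLS model gave the true SE of the TMCP contrast. Coverage was simulated with 800 runs per setting. With *r* = true SE / SE used, coverage should be close to 2Φ(1.96/*r*) − 1.

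| Setting | *r*, model-based | Coverage | *r*, clinician-clustered | Coverage |
|---|---|---|---|---|
| No turnover, any MA ICC | 1.00 | about 95% | about 1.0 | about 93-95% |
| Rotating, turnover 2-4%, MA ICC 0.05-0.20, no month terms | 1.35-4.6 | 85% to 33% | 1.3-2.6 | 87% to 55% |
| Same, with month terms | 1.07-2.2 | 94% to 63% | 1.07-1.9 | 93% to 70% |
| Paired with one clinician, turnover 2-4%, MA ICC 0.05-0.20, month terms | 1.07-2.0 | 93% to 67% | 1.01-1.02 | 93-97% (all paired settings) |

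The formula agrees: *r* = 1.35 gives 2Φ(1.45) − 1 = 85%, and *r* = 4.6 gives 2Φ(0.43) − 1 = 33%.

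**Step 4: one setting in full.** Rotating MAs, month terms, 30 visits per clinician-month, MA ICC 0.10, 6 MAs, 4% turnover. True SE 0.0189 against a model-based 0.0110, so *r* = 1.71. The formula gives 75% and simulation 73%. Clinician clustering covered 76%. Site clustering covered 83% with a z interval and 91% with *t* on 7 df and an 8/7 factor.

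**Step 5: site clustering.** Across settings, site-clustered z intervals covered about 83-90% whether the MA ICC was 0 or 0.20. That shortfall comes from having 8 clusters, not from MAs. With *t* on 7 df and the 8/7 factor, coverage was about 91-96%.

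**Step 6: modelling the MA.** A separate null simulation (rotating MAs, 2-3% monthly turnover, no calendar terms) gave type I error of 25-28% model-based, 22-23% clinician-clustered and 3-4% with an MA term. The MA term cut the true SE by about 33-48%. With month terms the gain is smaller: 8-30% in a 60-run check (6 MAs per site, 120 smoker visits per site-month, 2-3% turnover, MA ICC 0.02-0.10).

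**Step 7: QL contact.** Assume one accepted referral per clinician-month, a contact rate of 0.42 (the ceiling quoted in the Rationale for prior studies), 3% turnover, month terms and MA ICC 0.05-0.20. Then *r* is 1.01-1.05; at ICC 0.20 it is 0.0634/0.0604 = 1.05.

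**The case against.** The strongest reply is that the plan already specifies a robust variance, which does not need the within-cluster dependence to be modelled correctly. If it is clustered on site, MAs nested within sites are covered and only precision is lost. That is right. The weakness left is that the level is not stated.

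A second reply is that the documents report no MA/RN turnover. The only staffing disruptions described are a lost practice manager and a closed clinic. They also do not say that one MA/RN serves several clinicians. Both premises are assumptions, and without a changing mix the problem is nil.

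Third, the MA/RN does not own every step. Clinicians can order QL or FFS, TMCP itself has clinicians recommend quitting, and brief advice is not defined as an MA/RN entry. The point is therefore firm for Ask and Assess and for the MA/RN's scripted Advise. It is partial for Connect, and it applies to brief advice only so far as that is scored from the MA/RN's entry.

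Finally, the calculations use linear models, not the plan's logit GEE, and the largest figures omit calendar time. The direction does not depend on either choice, but the size does.

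**Conclusion.** The point holds conditionally. For the MA/RN-delivered outcomes the plan leaves out the person who performs the step and does not say how its robust variance is clustered. Under the assumed rotation and 2-4% monthly turnover, the true SE is 1.07 to 4.6 times the model-based SE and 1.07 to 2.6 times the clinician-clustered SE, with the lower values where month terms are fitted. Clinician-clustered intervals hold if each MA/RN works with one clinician; model-based intervals do not.

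A reader might infer that differences between MAs as such distort the TMCP contrast, that the trial's intervals are in fact far too narrow, or that the primary result is undermined. The documents support none of these. Stable differences cancel within site, the variance level and MA/RN staffing are unreported, and QL contact was hardly affected in the one sparse setting examined.

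**What to change.** In Statistical analyses, for Ask, Advise, Assess, Connect and any brief-advice measure built on the MA/RN entry:

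- Compute the robust variance at site level, the randomised unit, with a correction for 8 clusters, such as a bias-corrected sandwich and *t* with 7 df. State the calendar-time terms.
- Where a rooming-staff identifier exists for every visit, fit a mixed model with an MA/RN random effect crossed with clinician within site, and report it beside the site-plus-clinician model. Take the identifier from a source such as the vital-signs record. The tobacco entry is unsuitable, because it may be absent exactly when the step was not done, and dropping those visits would bias the rates.
- Say whether the main estimator is GEE or a mixed model, since the section mixes the two, and compare the two mixed models on the same scale.

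The cost is one more EHR field (assumed retrievable), a retrospective extraction because the section dates the analyses April 2019 to August 2020, and a more complex model. Intervals may be wider than naive ones. Against an uncorrected site-level z interval, *t* on 7 df with the 8/7 factor on the variance widens by (2.365/1.96) × √(8/7) = 1.207 × 1.069 = 1.29. No further patients, staff or visits are needed.
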